4. PATIENT SELECTION, ENROLLMENT, RANDOMIZATION, RESTRICTIONS, DISCONTINUATION AND WITHDRAWAL

Each patient must meet all of the inclusion criteria (Section 4.1) and none of the exclusion criteria (Section 4.2) for this study. Under no circumstances will there be exceptions to this rule.

4.1 Inclusion criteria

1. Histologically proven recurrent/metastatic squamous cell carcinoma arising from a previous head and neck primary site, and located within the head and neck region, lung mediastinum, lymph nodes, soft tissue metastases or bone, and who are not candidates for curative intent therapy.
2. Be ≥ 18 years old at the time of signing informed consent and have an actual body weight $> 40\text{kg}$.
3. Demonstrated disease progression during, or after discontinuation, of the most recent line of systemic therapy.

4. Have received any number lines of prior systemic therapy (including systemic therapy in the curative intent setting, and including a platinum containing regimen).
5. Have received an anti-PD1 or anti PDL1 monoclonal antibody.
6. Have a target lesion/s deemed suitable by the treating physicians for hypofractionated radiation therapy (HIGRT or SBRT) with the intent of palliation or prevention of symptoms. This lesion must be: a) 1-3 non overlapping sites in the head and neck region OR b) metastatic lesions outside the H&N region in the lung mediastinum, soft tissue metastases, lymph nodes or bone (a minimum of 1 and a maximum 5 lesions will be irradiated), provided there is no significant overlap between the lesions. Patients should have RECIST 1.1 criteria measurable disease in addition to the lesion/s treated with radiation. If the site/s of radiation were previously radiated to high dose RT (>50Gy), there should be >6 month time interval between the last dose of radiation and the start of radiation. .
7. Have the ability to tolerate required radiotherapy-related procedures(eg: lie flat and hold position for treatment) as determined by the treating physician
8. Be willing and able to provide written informed consent for the trial and comply with the study visit requirements
9. Have measurable disease based on RECIST 1.1. (in addition to the lesion/s that will be treated with hypofractionated radiation therapy)
10. Have provided tissue from an archival tissue sample or newly obtained core or excisional biopsy of a tumor lesion.
11. Have a performance status of 0 or 1 on the ECOG Performance Scale.
12. Demonstrate adequate organ function as defined in below, based on screening labs should be performed within 10 days of treatment initiation.

- Hemoglobin ≥ 9.0 g/dL
- Absolute neutrophil count (ANC) $\geq 1.5 \times 10^9/L$ (≥ 1500 per mm 3)
- Platelet count $\geq 100 \times 10^9/L$ ($\geq 100,000$ per mm 3)
- Serum bilirubin $\leq 1.5 \times$ institutional upper limit of normal (ULN). This will not apply to subjects with confirmed Gilbert's syndrome (persistent or recurrent hyperbilirubinemia that is predominantly unconjugated in the absence of hemolysis or hepatic pathology), who will be allowed only in consultation with their physician.
- AST (SGOT)/ALT (SGPT) $\leq 2.5 \times$ institutional upper limit of normal unless liver metastases are present, in which case it must be $\leq 5 \times$ ULN
- Serum creatinine CL > 60 mL/min by the Cockcroft-Gault formula (Cockcroft and Gault 1976) or by 24-hour urine collection for determination of creatinine clearance:

Males:

$$\text{Creatinine CL} = \frac{\text{Weight (kg)} \times (140 - \text{Age})}{72 \times \text{serum creatinine (mg/dL)}}$$

Females:

$$\text{Creatinine CL} = \frac{\text{Weight (kg)} \times (140 - \text{Age})}{72 \times \text{serum creatinine (mg/dL)}} \times 0.85$$

13. Evidence of post-menopausal status OR negative urinary or serum pregnancy test for female pre-menopausal patients. Women will be considered post-menopausal if they have been amenorrheic for 12 months without an alternative medical cause. The following age-specific requirements apply:
 - Women < 50 years of age would be considered post-menopausal if they have been amenorrheic for 12 months or more following cessation of exogenous hormonal treatments and if they have luteinizing hormone and follicle-stimulating hormone levels in the post-menopausal range for the institution or underwent surgical sterilization (bilateral oophorectomy, or hysterectomy).

- Women ≥ 50 years of age would be considered post-menopausal if they have been amenorrheic for 12 months or more following cessation of all exogenous hormonal treatments, had radiation-induced menopause with last menses >1 year ago, had chemotherapy-induced menopause with last menses >1 year ago, or underwent surgical sterilization (bilateral oophorectomy, bilateral salpingectomy or hysterectomy).

14. Female subjects of childbearing potential should have a negative urine or serum pregnancy within 72 hours prior to receiving the first dose of study medication. If the urine test is positive or cannot be confirmed as negative, a serum pregnancy test will be required.

15. Female subjects of childbearing potential should be willing to use 1 method of highly effective birth control or be surgically sterile, or abstain from heterosexual activity for the course of the study through 180 days after the last dose of study medication (Reference Section 7.1). Subjects of childbearing potential are those who have not been surgically sterilized or have not been free from menses for > 1 year.

16. Male subjects should agree to use an adequate method of contraception starting with the first dose of study therapy through 180 days after the last dose of study therapy.

17. Patient is ≥ 5 years free of another primary malignancy, except: a) if the other malignancy is basal cell carcinoma or cervical carcinoma in situ or b) if the other primary malignancy is not considered clinically significant and is requiring no active intervention

4.2 Exclusion criteria

The subject ***must be excluded*** from participating in the trial if the subject:

1. Has a body weight ≤ 40 kg at the time of enrollment
2. Is currently participating in or has participated in a study of an investigational agent or using an investigational device within 4 weeks of the first dose of treatment.
3. Has a target lesion/s for radiotherapy that is > 5 cm (> 50 cc) in greatest dimension

4. Has a target lesion/s in a region that previously received high dose RT (>50 Gy) demonstrating any of the following:
 - a. carotid artery encasement (> 180 degrees)
 - b. unprotected carotid artery (i.e. skin is directly over the carotid without intervening soft tissue, especially after prior neck dissection without a vascularized free flap) (a&b due to risk of carotid blow out)
 - c. skin infiltration by tumor (due to risk of fistula)
 - d. located in the larynx/hypopharynx primaries (due airway threat) treated with high dose radiation therapy (>50 Gy) within 6 months or less of trial enrollment
5. Any prior Grade ≥ 3 immune-related adverse event (irAE) while receiving a prior immunotherapy agent, or any unresolved irAE >Grade 1
6. Current or prior use of immunosuppressive medication within 14 days before the first dose of durvalumab or tremelimumab. The following are exceptions to this criterion:
 - Intranasal, inhaled, topical steroids, or local steroid injections (eg, intra articular injection)
 - Systemic corticosteroids at physiologic doses not to exceed 10 mg/day of prednisone or its equivalent
 - Steroids as premedication for hypersensitivity reactions (eg, CT scan premedication)
7. Has received a prior monoclonal antibody within 4 weeks prior to study Day 1 or who has not recovered (i.e., \leq Grade 1 or at baseline) from adverse events due to agents administered more than 4 weeks earlier.
8. Has received prior chemotherapy, targeted small molecule therapy, or radiation therapy within 2 weeks prior to study Day 1 or who has not recovered (i.e., \leq Grade 1 or at baseline) from adverse events due to a previously administered agent.
-Note: Subjects with \leq Grade 2 neuropathy are an exception to this criterion and may qualify for the study.

-Note: If subject received major surgery, they must have recovered adequately from the toxicity and/or complications from the intervention prior to starting therapy.

9. Has a known additional malignancy that is progressing or requires active treatment. Exceptions include basal cell carcinoma of the skin, squamous cell carcinoma of the skin, or in situ cervical cancer that has undergone potentially curative therapy.
10. Has known brain metastases or spinal cord compression unless the patient is stable (asymptomatic; no evidence of new or emerging brain metastases; and stable and off steroids for at least 14 days prior to start of study treatment). Following radiotherapy and/or surgery of the brain metastases patients must wait 4 weeks following the intervention and before initiating study treatment with imaging to confirm stability.
11. Has an active autoimmune disease requiring systemic treatment within the past 2 years or a documented history of clinically severe autoimmune disease, or a syndrome that requires systemic steroids or immunosuppressive agents. Subjects with vitiligo or resolved childhood asthma/atopy would be an exception to this rule. Subjects that require intermittent use of bronchodilators or local steroid injections would not be excluded from the study. Subjects with hypothyroidism stable on hormone replacement will not be excluded from the study.
12. Has evidence of current interstitial lung disease (ILD) or pneumonitis or a prior history of ILD or pneumonitis requiring oral or intravenous glucocorticoids
13. Has an active infection requiring systemic therapy.
14. Requires therapeutic anticoagulation or has known active bleeding diathesis
15. Has a history or current evidence of any condition, therapy, or laboratory abnormality that might confound the results of the trial, interfere with the subject's participation for the full duration of the trial, or is not in the best interest of the subject to participate, in the opinion of the treating investigator.
16. Has known psychiatric or substance abuse disorders that would interfere with cooperation with the requirements of the trial.

17. Is pregnant or breastfeeding, or expecting to conceive or father children within the projected duration of the trial, starting with the pre-screening or screening visit through 180 days after the last dose of trial treatment.
18. Has received prior therapy with an anti-Cytotoxic T-lymphocyte-associated antigen-4 (CTLA-4) antibody (including ipilimumab or any other antibody or drug specifically targeting T-cell co-stimulation or checkpoint pathways).
19. Has a known history of Human Immunodeficiency Virus (HIV) (HIV 1/2 antibodies).
20. Has evidence of acute or chronic hepatitis B, or hepatitis C
21. Has received a live vaccine within 30 days prior to the first dose of trial treatment.
22. Has a Mean QT interval corrected for heart rate (QTc) ≥ 470 ms calculated from 3 electrocardiograms (ECGs) using Fredericia's Correction
23. Has a history of primary immunodeficiency or an allogeneic organ transplant
24. Has a history of hypersensitivity to durvalumab or tremelimumab excipient
25. Known history of previous clinical diagnosis of tuberculosis
26. Uncontrolled intercurrent illness including, but not limited to symptomatic congestive heart failure, uncontrolled hypertension, unstable angina pectoris, cardiac arrhythmia, active peptic ulcer disease or gastritis, seizures

Procedures for withdrawal of incorrectly enrolled patients are presented in Section 4.3. Withdrawn patients will not be replaced.

4.3 Withdrawal of Subjects from Study Treatment and/or Study Permanent discontinuation of durvalumab and or tremelimumab

An individual subject will not receive any further investigational product if any of the following occur in the subject in question:

- The subject or legal representative (such as a parent or legal guardian) withdraws consent.
- Confirmation of PD and investigator determination that the subject is no longer benefiting from treatment with durvalumab + tremelimumab
- Any AE that meets criteria for discontinuation as defined in Section 10.3.
- Adverse event that, in the opinion of the investigator or the sponsor, contraindicates further dosing
- Subject noncompliance that, in the opinion of the investigator or sponsor, warrants withdrawal; e.g., refusal to adhere to scheduled visits
- Subject is determined to have met one or more of the exclusion criteria for study participation at study entry and continuing investigational therapy might constitute a safety risk
- Intercurrent illness that prevents further administration of treatment
- Investigator's decision to withdraw the subject
- The subject has a confirmed positive serum pregnancy test
- Noncompliance with trial treatment or procedure requirements
- The subject is lost to follow-up
- Completed 13 cycles of durvalumab
- Grade ≥ 3 infusion reaction

Subjects may withdraw consent at any time for any reason or be dropped from the trial at the discretion of the investigator should any untoward effect occur. In addition, a subject may be withdrawn by the investigator or the Sponsor if enrollment into the trial is inappropriate, the trial plan is violated, or for administrative and/or other safety reasons.

Subjects who are permanently discontinued from receiving investigational product will be allowed for safety per Appendix 2 or 3, including the collection of any protocol-specified blood specimens, unless consent is withdrawn or the subject is lost to follow-up or enrolled in another clinical study. All subjects will be followed for survival. Subjects who decline to return to the site for evaluations will be offered follow-up by phone every 3 months as an alternative.

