This is a single arm, open label, prospective study evaluating the safety and clinical efficacy of the combination of durvalumab, tremelimumab and hypofractionated palliative radiation therapy (using either hypofractionated image guided radiotherapy (HIGRT) or Stereotactic ablative Body Radiation Therapy (SBRT)) in patients who have previously received immunotherapy agents.

All patients enrolled will receive:

1. Durvalumab 1500 mg IV Q4W x 13 doses
2. Tremelimumab 75mg IV Q4W x 4 doses
3. Hypofractionated palliative radiation therapy using either (HIGRT) or (SBRT) to a total dose of 24Gy given in 3 fractions every other day over 1 week to lung, bone, lymph node, soft tissue metastases or mediastinal lesions. Radiotherapy is to be initiated 2 weeks after the first dose of durvalumab and tremelimumab.

Number of Centers: 1

Number of Subjects:

A maximum of 20 subjects will be enrolled.

Study Population:

The study aims to enroll patients with recurrent metastatic squamous cell carcinomas of the head and neck, who have received a prior immune checkpoint inhibitor, and who have a target lesion (either local/regional or distant metastatic site involving the lung and/or mediastinum and/or bone and/or soft tissue lesions and/or lymph nodes , that requires local control for palliation, as determined by a multidisciplinary team.

Inclusion Criteria:

1. Histologically proven recurrent/metastatic squamous cell carcinoma arising from a previous head and neck primary site, and located within the head and neck region, lung mediastinum bone, , soft tissue, lymph nodes, and who are not candidates for curative intent therapy.
2. Be ≥ 18 years old at the time of signing informed consent and have an actual body weight $> 40\text{kg}$.
3. Demonstrated disease progression during, or after discontinuation, of the most recent line of systemic therapy.
4. Have received any number lines of prior systemic therapy (including systemic therapy in the curative intent setting, and including a platinum containing regimen).
5. Have received an anti-PD1 or anti PDL1 monoclonal antibody.

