The subject **must be excluded** from participating in the trial if the subject:

1. Has a body weight ≤ 40 kg at the time of enrollment
2. Is currently participating in or has participated in a study of an investigational agent or using an investigational device within 4 weeks of the first dose of treatment.
3. Has a target lesion/s for radiotherapy that is > 5 cm (> 50 cc) in greatest dimension
4. Has a target lesion/s in a region that previously received high dose RT (>50 Gy) demonstrating any of the following:
 - a. carotid artery encasement (> 180 degrees)
 - b. unprotected carotid artery (i.e. skin is directly over the carotid without intervening soft tissue, especially after prior neck dissection without a vascularized free flap) (a&b due to risk of carotid blow out)
 - c. skin infiltration by tumor (due to risk of fistula)
 - d. located in the larynx/hypopharynx primaries (due airway threat)
 - e. treated with high dose radiation therapy (>50 Gy) within 6 months or less of trial enrollment
5. Any prior Grade ≥ 3 immune-related adverse event (irAE) while receiving a prior immunotherapy agent, or any unresolved irAE $>$ Grade 1
6. Current or prior use of immunosuppressive medication within 14 days before the first dose of durvalumab or tremelimumab. The following are exceptions to this criterion:
 - Intranasal, inhaled, topical steroids, or local steroid injections (eg, intra articular injection)
 - Systemic corticosteroids at physiologic doses not to exceed 10 mg/day of prednisone or its equivalent
 - Steroids as premedication for hypersensitivity reactions (eg, CT scan premedication)
7. Has received a prior monoclonal antibody within 4 weeks prior to study Day 1 or who has not recovered (i.e., \leq Grade 1 or at baseline) from adverse events due to agents administered more than 4 weeks earlier.

8. Has received prior chemotherapy, targeted small molecule therapy, or radiation therapy within 2 weeks prior to study Day 1 or who has not recovered (i.e., \leq Grade 1 or at baseline) from adverse events due to a previously administered agent.
 - Note: Subjects with \leq Grade 2 neuropathy are an exception to this criterion and may qualify for the study.
 - Note: If subject received major surgery, they must have recovered adequately from the toxicity and/or complications from the intervention prior to starting therapy.

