8.1.1 Screening Phase

Screening procedures will be performed up to 28 days before Day 1, unless otherwise specified. All subjects must first read, understand, and sign the IRB/REB/IEC-approved ICF before any study-specific screening procedures are performed. After signing the ICF, completing all screening procedures, and being deemed eligible for entry, subjects will be enrolled in the study.

Procedures that are performed prior to the signing of the ICF and are considered standard of care may be used as screening assessments if they fall within the 28-day screening window.

The following procedures will be performed during the Screening Visit:

- Informed Consent
- Review of eligibility criteria
- Medical history and demographics
- Complete physical exam
- ECOG Performance Status
- Vitals signs, weight
- 12-lead ECG (in triplicate [2-5 minutes apart])
- Archived tissue or tumor biopsy
- Review of prior/concomitant medications
- Imaging by CT/MRI
- Clinical laboratory tests for:
 - Hematology (see Table 3)
 - Clinical chemistry (see Table 4)
 - TSH with reflexive free T4
 - Coagulation (PT, aPTT, INR)
 - Creatinine Clearance
 - Serum or urine pregnancy test (for women of childbearing potential only)
 - Urinalysis (see Table 7)

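### Exclusion 4 differs between the synopsis and Section 4.2: a larynx or hypopharynx target given more than 50 Gy over six months ago is excluded by one list and not by the other

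*Combined protocol and SAP*

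**What the plan says.** Exclusion 4 appears in the synopsis and in Section 4.2 with the same opening: the target lies in a region that earlier received more than 50 Gy, and any one of the listed features excludes the patient. Sub-items a to c (carotid encasement, unprotected carotid, skin infiltration) also agree.

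The lists part after that. In the synopsis, 4d is "located in the larynx/hypopharynx primaries (due airway threat" and ends there. A separate 4e follows: "treated with high dose radiation therapy (>50 Gy) within 6 months or less of trial enrollment".

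Section 4.2 has no 4e. The same words run on as a single 4d: "located in the larynx/hypopharynx primaries (due airway threat) treated with high dose radiation therapy (>50 Gy) within 6 months or less of trial enrollment".

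The opening of Section 4 says which list governs: "Each patient must meet all of the inclusion criteria (Section 4.1) and none of the exclusion criteria (Section 4.2) for this study". It allows no exceptions and does not say what happens if the synopsis differs.

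Inclusion 6, in both lists, deals with any site previously given more than 50 Gy: "there should be >6 month time interval between the last dose of radiation and the start of radiation". It admits one to three head and neck sites as targets and has no larynx or hypopharynx restriction.

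**The concern.** The reason given for the larynx/hypopharynx item is airway threat. In the synopsis, location within a previously irradiated region is enough to exclude. In Section 4.2 as it reads, location counts only if the earlier high-dose course was recent. Staff following Section 4.2 would admit a patient whom the synopsis excludes on safety grounds.

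The trial's primary objective is safety, and Section 1.4.2.5 relies on the eligibility criteria to limit radiation toxicity. Section 1.1.5 puts morbidity after stereotactic re-irradiation at 10-50% and mortality at 1-5%. Those are general re-irradiation figures, not laryngeal ones, but they show why the plan restricts these targets. The same question can return at retreatment, because Section 5.2.2 requires eligibility to be met again and leaves further radiotherapy to the physician.

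**Working it through.** The plan gives no figure on this point, so the check compares two rules. Take a target in a region given more than 50 Gy, with none of features a to c, and classify it by site and by time from that radiation to enrollment.

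| Case | Synopsis item 4 | Section 4.2 item 4 | Does inclusion 6 settle it? |
|---|---|---|---|
| 1. Larynx/hypopharynx, 6 months or less | Excluded (4d, 4e) | Excluded (4d) | No difference to settle |
| 2. Larynx/hypopharynx, over 6 months | Excluded (4d) | Not excluded | No: the interval is met |
| 3. Other site, 6 months or less | Excluded (4e) | Not excluded | Largely |
| 4. Other site, over 6 months | Not excluded | Not excluded | No difference to settle |

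**Case 2 is the conflict.** The patient satisfies the interval in inclusion 6, and no other criterion is specific to the airway.

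**Case 3 is minor.** Inclusion 6 counts to the start of study radiation, while synopsis 4e counts to enrollment. The lists therefore differ only for patients who pass six months between those dates. The length of that gap follows from three statements:

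- Section 8.1.1: "After signing the ICF, completing all screening procedures, and being deemed eligible for entry, subjects will be enrolled in the study".
- Section 4.1, item 12: "screening labs should be performed within 10 days of treatment initiation".
- Synopsis, study design: "Radiotherapy is to be initiated 2 weeks after the first dose of durvalumab and tremelimumab".

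Enrollment therefore falls 0 to 10 days before the first dose (an inference from the first two), and radiation starts 14 days after it. Before visit windows, the gap is:

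- shortest: 0 + 14 = 14 days
- longest: 10 + 14 = 24 days

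Taking six months as 183 days, the oldest last dose in case 3 is 183 days before enrollment. The most recent that inclusion 6 would let through is 183 − 14 = 169 or 183 − 24 = 159 days before. This is the oldest end of the six-month window, and it does not bear on case 2.

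**What still protects a case 2 patient.** Section 5.3.3 sets organ dose limits for targets with no prior radiation, then says they do not apply to re-irradiation, where the treating physician decides. Every case 2 patient is a re-irradiation case. The limits would help little anyway: the trachea has a figure, but the larynx has none and falls under the general instruction for remaining organs. What is left is general:

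- the six-month interval
- the lesion size limit (exclusion 3)
- features a to c of exclusion 4
- investigator judgement (exclusion 15)
- the treating physicians' view that the target is suitable (inclusion 6)
- the multidisciplinary decision that local control is needed (synopsis, study population)

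**The case against.** The strongest objection is that there may be no error in the plan. The two versions differ by one list label and a line break, and such things can be lost when a PDF is read into text. List layout is unsteady elsewhere: the notes under exclusion 8 are set differently in the two lists, and a sentence in the sectioning instructions of Section 8.3.2 is spliced. This possibility stands and is why the fix begins with the source file. It is not shown, however. Section 4.2 keeps labels a to d, the words run on within one line, and the merged sentence is grammatical enough to be applied as a single rule.

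A second objection is that Section 4 names the operative list, so the formal rule is known. That is so, but it makes the more permissive wording the operative one for this patient without showing that it was meant.

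Three stronger readings are tempting, and the documents do not support them:

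- A reader might infer that the two-item version must be the intended one because the merged 4d adds almost nothing to inclusion 6. Synopsis 4e repeats the dose threshold and overlaps inclusion 6 too, and duplication is common in these lists (body weight and measurable disease each appear twice). Redundancy does not settle intent.
- A reader might infer that Section 4.3 would stop study drug in these patients. That clause applies when continuing drug may be unsafe. The airway risk here comes from three fractions of radiation, so it has little bearing.
- A reader might want inclusion 6 and 4e counted from one date. They can stand together, and moving 4e to the start of radiation would loosen it. That is a separate preference.

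**Conclusion.** The conflict holds on the text as it reads. For a larynx or hypopharynx target given more than 50 Gy over six months before enrollment, the synopsis excludes and Section 4.2 does not. Inclusion 6 leaves the difference in place, and the remaining safeguards are not airway-specific. For other sites the lists differ only in the 14 to 24 day margin shown above.

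The documents give no count of affected patients, so no number of patients or airway events is claimed. A reader might infer that patients have been wrongly enrolled or harmed, and nothing in the documents shows that. Sample size, error rates and analyses are unaffected.

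The conclusion assumes that item e is truly absent from Section 4.2. If the source file shows it, the point falls away. Which wording was intended is for the investigators to say. Even so, two mandatory safety rules that disagree should be reconciled.

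**What to change.** Look at the source file of Section 4.2 first. If a separate item e is there, nothing more is needed.

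If it is absent, restore two items in Section 4.2 to match the synopsis:

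- 4d: larynx or hypopharynx location in a region given more than 50 Gy, with no time limit.
- 4e: more than 50 Gy within six months or less before enrollment, at any site.

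If the investigators confirm that the narrower rule was intended, correct the synopsis instead. Keep the existing date anchors. Check any patients already enrolled against the corrected list; there are at most 20, apart from run-in replacements.

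The cost is one wording amendment, submitted to the IRB as Section 12.4 requires, and a short record check. Restoring two items makes eligibility slightly narrower than Section 4.2 now states. The sample size and analysis stay as they are.
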